3.3 ENDPOINTS

3.3.1 Immunogenicity

The primary immunogenicity endpoint is the proportion of participants achieving a four times or greater increase in NAC by Week 4 compared with Week 0. A positive response will be defined as achieving this level of increase in at least 50% of the participants for botulinum toxin type A and type B.

The secondary immunogenicity endpoints are as follows:

- The proportion of participants achieving a two times increase in the area under the plasma concentration-time curve between Week 0 and Week 12 in NAC in comparison to a straight-line extension of the Week 0 NAC to Week 12. A

positive response will be defined as achieving this level of increase in at least 50% of the participants for botulinum toxin type A and type B.

- The proportion of participants achieving a three times or greater increase in NAC by Week 4 compared with Week 0. A positive response will be defined as achieving this level of increase in at least 50% of the participants for botulinum toxin type A and type B.

3.3.2 Safety

Primary safety endpoints will be collected over a 12-week period and will be as follows:

- Frequency of injection site reactions and systemic reactions that are characterized as severe during the 0-7 day diary collection period.
- Frequency of injection site reactions and systemic reactions that are characterized as serious adverse events (SAEs) [Definitions for local injection site reactions are in Section 6.9 and systemic reactions are located in Appendix B. Definition of SAE is located in Section 6.1]
- Participant incidence of treatment-related serious adverse events (Adverse event toxicity tables are located in [Appendix B](#))
- Participant incidence of serious NOCIs
- Clinically significant changes from baseline health resulting in serious adverse events
- Clinically significant changes in hematology between screening and Week 4 resulting in severe or serious adverse events

3.3.3 Exploratory

The exploratory endpoint will be the volume of source plasma containing neutralizing antibodies against botulinum toxin type A and type B collected by plasmapheresis for use in BabyBIG manufacture.

3.4 RANDOMIZATION AND BLINDING

There will be no randomization or blinding of participants for safety assessments in this study.

3.5 REPLACEMENT OF DROPOUTS

Dropouts will not be replaced in this study.

4.0 DRUGS AND DOSAGES

4.1 IDENTIFICATION AND DESCRIPTION OF INVESTIGATIONAL PRODUCT

4.1.1 Investigational Product

rBV A/B is manufactured by DynPort Vaccine Company LLC, a GDIT Company (Frederick, Maryland). The procedure used to manufacture the active ingredient of rBV A/B is described below.

[figure not shown]
The recombinant botulinum neurotoxin antigens are expressed from synthetic genes encoding the carboxy-terminal region of the botulinum neurotoxins (BoNT) heavy-chains [rBoNT(Hc)] of BoNT/A and BoNT/B, designated Antigen A and Antigen B. These fragments are from the binding domain of the heavy-chain and do not have neurotoxic activity. Antigen A and Antigen B are expressed in the methylotrophic yeast *Pichia pastoris* as 50 kDa and 52 kDa proteins, respectively. Antigen A is derived from the BoNT/A1 expressed by *Clostridium botulinum* strain NCTC 2916 (Group I, proteolytic), and Antigen B is derived from BoNT/B1 expressed by *C. botulinum* strain Danish (Group I, proteolytic). These proteins have been expressed individually by using a methanol induction system from synthetic genes introduced into *P. pastoris*. The bulk antigens were manufactured at high purity (each antigen purified drug substance is >95% pure), formulated and combined in a 1:1 ratio based on mass (in micrograms) to produce the final drug product.

The formulation used for this study will have 40 micrograms (μ g) total antigen (20 μ g Antigen A and 20 μ g Antigen B) with 100 mM sodium chloride, 15 mM sodium phosphate, and 50 mM sodium acetate with AlhydrogelTM (0.2% weight per volume) balanced to a pH of 5.5 for a total dose volume of 0.5 mL.

4.1.2 Labeling

Each vial in Lot D1200138 will be labeled as shown in Figure 1.

Figure 1. Sample vial label.

4.2 DOSING INSTRUCTIONS AND SCHEDULE

Participants will receive a 0.5 mL intramuscular injection of rBV A/B in the deltoid muscle, preferably in the nondominant arm. The injection will be administered by the investigator or delegated site personnel. Site personnel will document the time of the injection in the electronic case report form (eCRF). Each vial should be visually inspected for particulate matter, discoloration, signs of adulteration, or contamination before administration. If the product appears discolored or has visible particulate matter, it should not be used and both the study monitor and principal investigator should be notified. If the investigational product in the vial is suspect, it should not be dispensed or administered. Instead, a new dose should be obtained, inspected, and the dose withdrawn then administered. The occurrence of such an event should be recorded in the ISF (investigator site file).

Each vial will be prepared by swirling gently immediately before use. Approximately 0.5 to 0.6 mL of investigational product will be drawn into a sterile, 1 mL latex-free tuberculin syringe (Becton Dickinson & Co.) or equivalent with a sterile, 21-gauge, 1-inch BD PrecisionGlide™ Needle (Becton Dickinson & Co.) or equivalent. To ensure a full dose is able to be drawn from each vial, the vial may need to be inverted with the bevel of the needle inserted just above the rubber stopper. The date, time, and administrator's initials will be recorded in the participant's source record and on the Investigational Product Accountability Log upon administering the investigational product to the participant. In addition, the

site of vaccination (e.g., deltoid muscle of left arm) will be recorded in the participant's source medical record.

4.3 STORAGE AND HANDLING OF INVESTIGATIONAL PRODUCT

All vials will be stored at 2°C to 8°C (35.6°F to 46.4°F) in a secure storage location. The refrigerator temperature will be recorded continuously and monitored daily. The investigational product must not be frozen. A copy of the temperature logs for the storage refrigerator must be filed in the site study files to document appropriate storage conditions.

The principal investigator must ensure that accurate records of receipt of all vaccine, including date of receipt, are maintained throughout the study. In addition, accurate records must be kept regarding when and how much vaccine was used.

Study personnel must not destroy or throw away any vial of vaccine, including empty, damaged, or partially used ones. At the completion of the study, to satisfy regulatory requirements regarding drug accountability, all vaccine will be reconciled and the study monitor will verify that the remaining vials have been either returned to designee as determined by the sponsor-investigator or destroyed following the sponsor-investigator's instructions.

4.4 DOSE STOPPING RULES

4.4.1 Individual Participant Stopping Rules

Because only one dose of vaccine is administered per participant, there will be no individual participant stopping rules to preclude further vaccination.

Participants who develop a Grade 3 (or higher) immediate hypersensitivity reaction to the vaccine will be counselled by the investigator that future exposure to rBV A/B would not be advisable.

4.4.2 Study Stopping Rules

For this study, the following are the dose stopping rules; and, if they occur, all dosing will stop, the DSMB (Section 6.10) will convene, review the data collected, and make a recommendation for continued dosing.

- If any participant has an SAE (see Section 6.1 for a definition) considered possibly, probably, or definitely related to the vaccine
- Two or more participants with a Grade 3 (severe) or higher similar hematologic abnormality, considered possibly, probably or definitely related to the vaccine
- Two or more participants with neuromuscular AEs considered possibly, probably or definitely related to the vaccine

If the DSMB determines that an SAE was a vaccine-related SAE, then the sponsor-investigator will provide the DSMB's recommendation along with the SAE report to the FDA and seek the Agency's guidance on resuming the study.

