Safety considerations: Participants will be monitored for serious adverse events after vaccination throughout the 12-week study period and at the Week 26 phone call follow-up. Administration site reactions and systemic reactions will be monitored with a diary provided to collect information, including diameter of any swelling and redness around the injection site and any generalized symptoms between Week 0 and Week 1 in order to determine if any severe reactions or serious adverse events occurred during this 1-week period post-vaccination. All severe local and systemic reactions will be recorded in the electronic case report form (eCRF). Hematology, serum chemistry, and urinalysis specimens will be collected at screening, and repeat hematology at Week 4 for monitoring of any clinically significant changes that result in a severe or serious AE. Clinically significant changes in hematology that result in a severe or serious AE will be recorded on the eCRF. Female participants of childbearing potential will have a urine pregnancy test at screening and again at Week 0 prior to receipt of the vaccine. Source plasma collection will occur for eligible donors at licensed collection locations. If the participant fails to meet donor criteria at any time during the plasmapheresis period, the participant will continue to be followed for serious adverse events according to the study schedule. Participants will be contacted by phone at Weeks 1, 4, and 10. At Week 26, participants will be queried for occurrence of serious adverse events and serious new onset chronic illnesses (NOCIs), which will be recorded by the investigator (or designee) on serious adverse events recording sheets and entered in the eCRF. Vital signs will be monitored at screening, Week 0 (vaccine visit), and at each plasma collection visit.

STUDY SYNOPSIS (continued)

Name of sponsor company: California Department of Public Health (CDPH)
Name of investigational product: Recombinant Botulinum Vaccine A/B (rBV A/B)
Names of active ingredients: Recombinant Botulinum Antigen A and Antigen B adsorbed to 0.2% (wt/vol) Alhydrogel™
Statistical methods: The data will be summarized in tables listing the mean, standard deviation or standard error, median, minimum, maximum, and number of participants for continuous data, or in tables listing count and percentage for categorical data, where appropriate.

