The immunogenicity parameters are NACs for botulinum toxin type A and type B. These NAC parameters will be analyzed utilizing a validated mouse neutralization assay.
Summaries of local and systemic severe AEs and SAEs related to vaccination (collected in the 7-day diaries) will be produced in tables, by category and severity.
Summaries of clinically significant changes in hematology between screening and Week 4 resulting in a severe or serious AE will be listed.
SAE data will be listed individually and summarized by system organ class and preferred terms and by severity and relatedness.
SAE data of NOCIs will be listed individually and summarized by system organ class and preferred terms and by severity and relatedness.
No formal sample size calculations will be done.

TABLE OF CONTENTS

	Page
TITLE OF STUDY:	1
1.0 INTRODUCTION.....	16
1.1 BACKGROUND.....	16
1.2 STUDY RATIONALE.....	17
1.3 DOSE RATIONALE	17
2.0 OBJECTIVES	19
2.1 IMMUNOGENICITY	19
2.2 SAFETY.....	19
2.3 EXPLORATORY	19
3.0 STUDY DESIGN.....	20
3.1 BASIC DESIGN CHARACTERISTICS	20
3.2 STUDY POPULATION	20
3.2.1 Inclusion Criteria	20
3.2.2 Exclusion Criteria	22
3.3 ENDPOINTS	24
3.3.1 Immunogenicity.....	24
3.3.2 Safety.....	25
3.3.3 Exploratory	25
3.4 RANDOMIZATION AND BLINDING	26
3.5 REPLACEMENT OF DROPOUTS.....	26
4.0 DRUGS AND DOSAGES	27
4.1 IDENTIFICATION AND DESCRIPTION OF INVESTIGATIONAL PRODUCT	27
4.1.1 Investigational Product	27
4.1.2 Labeling	28
4.2 DOSING INSTRUCTIONS AND SCHEDULE.....	28
4.3 STORAGE AND HANDLING OF INVESTIGATIONAL PRODUCT	29
4.4 DOSE STOPPING RULES.....	29
4.4.1 Individual Participant Stopping Rules	29
4.4.2 Study Stopping Rules	29
4.5 CONCOMITANT MEDICATIONS	30
5.0 EXPERIMENTAL PROCEDURES.....	31
5.1 OVERVIEW: SCHEDULE OF TIME AND EVENTS	31
5.2 MEASUREMENTS AND EVALUATIONS.....	34
5.2.1 Screening Period (between Days -7 and -1)	34
5.2.2 Treatment Period (12 weeks, plasma donors; 4 weeks non-plasma donors)	35
5.2.3 Final Study Follow-up (Day 182, Week 26).....	40
6.0 PROCEDURES FOR HANDLING SERIOUS ADVERSE EVENTS.....	41
6.1 DEFINITION OF A SERIOUS ADVERSE EVENT	41
6.2 RECORDING SERIOUS ADVERSE EVENTS	42

TABLE OF CONTENTS (continued)

	Page
6.3 ASSESSMENT OF SEVERITY	43
6.4 ASSESSMENT OF CAUSALITY.....	44
6.5 EXPECTEDNESS OF ADVERSE EVENTS	46
6.6 REPORTING OF SERIOUS ADVERSE EVENTS	46
6.7 FOLLOW-UP OF SERIOUS ADVERSE EVENTS	48
6.8 LOCALIZED AND SYSTEMIC INJECTION SITE REACTIONS	48
6.9 DATA AND SAFETY MONITORING BOARD	49
6.10 PREGNANCY	49

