Diary review			X					
Serious adverse event collection ^r		X	X	X	X		X	X
Concomitant medication information	X ^t		X ^s	X ^s	X ^s		X ^s	X ^s
Phone call			X	X	X			X

HBV = hepatitis B virus; HCV = hepatitis C virus; HIV = human immunodeficiency virus; NAC = neutralizing antibody concentration; rBV A/B = recombinant botulinum vaccine A/B.

a. Week 1, Week 4, and Week 10 Follow-up Calls must occur with ± 3 days of the scheduled time.

b. Final Study Visit will be an on-site visit at Week 4 for participants who opt not to participate or who have been determined to be ineligible for donation for the entire study. All final assessments occurring at Week 12 will occur at Week 4 for these participants.

c. Extension of plasmapheresis for up to 14 weeks is optional

- d. Final on-site Study Visit must occur within \pm 7 days of the scheduled time.
- e. Final follow-up call for safety must occur within \pm 1 week of the scheduled time.
- f. Plasmapheresis-specific informed consent formed will be signed at the source plasma center.
- g. Physical examination will be performed as part of source plasma donor screening at the plasma collection center
- h. Female participants of childbearing potential must have a negative pregnancy test within 24 hours prior to vaccination.
- i. Participants will have vital signs taken twice at Visit 1: prior to injection, and 30 minutes (\pm 5 minutes) after receiving the injection.
- j. HIV, HBV, and HCV tests will be performed on each donated source plasma unit
- k. Results from screening tests must be available before Vaccination Visit
- l. Study participants will go to central lab or plasma center for this draw (not an on-site visit).
- m. Baseline NAC sample must be collected before rBV A/B injection and before plasmapheresis
- n. Participants not donating plasma must go to site for NAC collection within \pm 3 days of the scheduled time.
- o. May occur up to twice a week for up to 14 weeks (if hemoglobin and total protein remain within acceptable range) following vaccination with rBV A/B.
- p. At this visit, participants will be monitored for at least 30 minutes after injection for a possible reaction.
- q. In the diaries, participants record adverse events in order to determine SAE, oral temperature and injection site information.
- r. Only serious adverse events and new onset chronic illnesses are to be queried for and collected

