6.6 ADVERSE EVENTS OF SPECIAL INTEREST

Adverse events of special interest that are particularly specific to this study will be collected, assessed and recorded in the eCRF as an AE. These events of special interest will be collected in addition to the SAEs described in Section 6.1 and include the following clinical situations (see Section 3.3.2):

- Frequency of injection site reactions and systemic reactions among the study participants that are assessed as severe between Day 0 and 7 will be captured as an AE.
- Clinically significant changes in hematology between screening and Week 4 that are assessed as severe will be captured as an AE.

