8.2.5 Safety Analysis

The safety analysis will use the safety population.

Localized and systemic severe AEs and SAEs collected from the Week 1 telephone call will be summarized by category and severity. A point estimate of incidence, with 95% confidence limits will be computed and reported (not coded into the Medical Dictionary for Regulatory Activities [MedDRA] terminology or assessed for relatedness). The time period summarized will include throughout the study as a whole and again within Days 0 through 7. For tables summarizing severity, the

highest reported severity grade will be used. In addition, the average duration, by category, will be summarized.

All other SAE data will be listed individually and summarized by system organ class and preferred terms for each treatment group. When calculating the incidence of SAEs, each SAE based on preferred terminology from MedDRA will be counted only once for a given participant. If the same SAE occurs on multiple occasions in a participant, the occurrence with the highest severity and highest causality relationship to the vaccine will be reported. If two or more SAEs are reported as a unit, the individual terms will be reported as separate experiences.

Treatment-emergent abnormal values that occur prior to the end of the study will be summarized. Laboratory abnormalities will be assessed for relatedness. Treatment-emergent changes from normal to abnormal values in key laboratory parameters will be identified.

Presentation of relatedness in tables will be based on the investigator's assessment.

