8.2 CLINICAL LABORATORY EVALUATIONS

Samples for hematology, serum chemistry, and urinalysis will be collected at screening. Hematology samples will also be collected at Week 4.

Treatment-emergent abnormal hematology values at Week 4 will be summarized. Hematology laboratory abnormalities will be assessed for relatedness and may be presented by relatedness in tables based on the investigator's assessment.

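### Stopping rule 3 halts dosing on two related neuromuscular AEs of any grade, but the collection, causality and reporting sections do not secure the non-serious events that it needs

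*Protocol*

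**What the plan says.** Protocol 4.4.2 lists three conditions that stop all dosing and convene the DSMB: one related SAE; two or more participants with a similar related hematologic abnormality of Grade 3 or higher; and "Two or more participants with neuromuscular AEs considered possibly, probably or definitely related to the vaccine". The third has no grade threshold, although the second, beside it, has one. Table 11 in Appendix B grades neuromuscular events from Grade 1, where muscle weakness may be purely subjective.

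The texts that would feed the third rule are these:

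- **Causality.** Section 6.4 obliges the investigator to rate each SAE. Section 8.2.5 says that severe local and systemic reactions from the Week 1 call are "not coded into the Medical Dictionary for Regulatory Activities [MedDRA] terminology or assessed for relatedness". The synopsis, under Statistical methods, speaks of summarizing "severe AEs and SAEs related to vaccination (collected in the 7-day diaries").
- **Laboratory findings.** Relatedness is stated explicitly here: "Laboratory abnormalities will be assessed for relatedness" (Protocol 8.2.5) and "Hematology laboratory abnormalities will be assessed for relatedness" (SAP 8.2).
- **eCRF entry.** The synopsis, in its account of the first week, says: "All severe local and systemic reactions will be recorded in the electronic case report form (eCRF"). Section 6.6 covers reactions "assessed as severe between Day 0 and 7 will be captured as an AE", and severe hematology changes up to Week 4. SAP 8.1 repeats those two categories.
- **Collection.** Note r to Table 1 reads: "Only serious adverse events and new onset chronic illnesses are to be queried for and collected".
- **Reporting.** Section 6.7 sends SAEs to the medical monitor and sponsor-investigator within 24 hours, and to the DSMB.

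**The concern.** A halting rule works only if someone is obliged to notice, rate and count the events that it names. Here the rule covers neuromuscular AEs of every grade, while the sections that tell sites what to collect, rate and pass on are written for SAEs, with two narrow additions. A site that followed those sections literally could hold a relevant event in its source notes without rating it or telling anyone outside the site.

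The stake is participant safety while vaccination continues. The vaccine is derived from botulinum neurotoxin fragments, and the protocol chose to stop on two related neuromuscular events however mild. If one such event occurs at each of the two sites, the halt depends on somebody seeing both.

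**Working it through.** The plan states no operating characteristic for its stopping rules, so there is no figure to reproduce. The check sets the texts side by side.

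**1. Which events does rule 3 add?** If either event of a pair were a related SAE, rule 1 would already have stopped dosing. Rule 3 therefore changes the outcome only when both events are non-serious.

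**2. Must a non-serious neuromuscular AE be rated for causality?** Section 6.4 says each SAE; its later sentence about every event is tied to sending the SAE report. Outside SAEs, an explicit statement exists only for laboratory abnormalities, which serves rule 2. For severe Week 1 reactions, 8.2.5 points the other way.

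**3. Must it be entered in the eCRF?**
- Severe, Day 0-7: yes, under 6.6. Section 6.9 includes neuromuscular events among the systemic reactions.
- Grade 1-2 at any time: no clear requirement. Section 6.1 puts clinical complaints in source documents and serious events in the eCRF. SAP 8.5 carries significant diary data into the AE data but does not define significant.
- Non-serious Grade 3 after Day 7: no clear requirement. At the Week 4 and 10 calls, 5.2.2.5 has staff ask plasma donors about worsening AEs and systemic reactions, but enters only the serious ones.

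**4. Must it be reported onward?** Sections 6.7 and 6.8 cover SAEs. Section 6.5 mentions receipt of an initial AE report, but no text says when a non-serious AE is reported. Non-serious rule 2 events lack a report line too.

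**5. Do the collection instructions agree?** Note r restricts querying and collection to SAEs and new onset chronic illnesses. Appendix E has staff query the participant's AE sheet at visits and at Weeks 1, 4, 10 and 26, and 5.2.2.5 asks more than note r allows.

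**6. Do the forms match the text?** Section 6.9 says the diary collects the severity of, among others, muscle weakness, breathing difficulties and neuromuscular TEAEs. The Appendix C form has 9 systemic items, all Yes/No, and none of these three is among them. Appendix E names 11 neuromuscular symptoms; none appears by name on Appendix C. Appendix E has a severity column and so partly fills the gap. Its duration is unclear: 5.2.2.1 issues it for 7 days, 5.2.2.3 has it used between calls, and the form refers to the whole study.

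**7. An example.** A donor notes mild arm weakness in Week 3 on Appendix E. Staff hear of it, at the latest at the Week 4 call, and the sheet has a line for review by the site investigator or a designee. No operating section then requires a relatedness rating, eCRF entry or notice to whoever counts across sites. A similar case at the other site could follow the same path.

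**The case against.** A reader might infer that rule 3 cannot fire, or that no one would ever judge relatedness. The documents do not support that.

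- Applying the rule requires a relatedness judgement, and Table 3 defines its causality terms for adverse events generally.
- Appendix E tells participants to seek care and notify contacts who are available at all hours if any listed neuromuscular symptom appears. The contacts' roles are redacted. The form appears common to both sites, so they may be central, and the redaction cannot be counted against the plan.
- The parenthesis in 8.2.5 can be read as a note on tabulation. It also covers SAEs, which 6.4 does require to be rated, and its remark on MedDRA coding does not match SAP 8.1.
- Section 6.6 says special-interest events are assessed, and SAP 8.1 allows AE summaries by causality. Neither says that these reactions receive a causality rating.
- Note r is attached to the SAE collection row, so it may not have been meant to bar other collection.
- Under 6.10 the DSMB sees safety data quarterly, and SAP 3.6 leaves its displays to a separate document.

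These points stand as far as they go: the event can enter the study, and an attentive investigator can trigger the rule. They do not create a duty to rate, record or pass on a non-serious event. Quarterly review is a partial backstop only. It can come weeks after an event, and it can show only what was captured.

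A reader might also want a probability that a halt is missed. The documents give no rate of related neuromuscular AEs and no capture fraction, so any such figure would rest wholly on assumption.

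**Conclusion.** The point holds as a mismatch between a safety halting rule and the sections that should supply it. Rule 3 can fire by investigator judgement, but the plan does not assure that non-serious related neuromuscular AEs are rated and counted across the two sites. Only severe Day 0-7 reactions have a clear eCRF requirement, and even those have no clear causality requirement and no onward report.

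The size is procedural and cannot be expressed as an error rate. It matters only while dosing continues at either site, and no planned immunogenicity analysis is affected. The conclusion assumes that no unseen document, such as the study procedure manual or the DSMB display specification, already sets a reporting path, and that the redacted Appendix E contacts do not keep a central count. If either does, the remaining work is to align the protocol text. The point should be clarified before vaccination starts.

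**What to change.** Keep rule 3 as written and give it an input:

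- Add neuromuscular AEs of any grade to the special-interest events in Protocol 6.6 and SAP 8.1, with eCRF entry, Table 11 grading and an investigator causality rating.
- Require prompt reporting of these events to the sponsor-investigator and DSMB while dosing continues at either site. The 24-hour line in Table 4 can be reused.
- Align 6.4, 6.7, note r and 8.2.5 with this, and resolve the difference between 8.2.5 and the synopsis on relatedness.
- Either add muscle weakness and the Appendix E symptoms, with severity, to the Appendix C diary, or have 6.9 point to Appendix E for them.
- State one duration for the Appendix E sheet in 5.2.2.1, 5.2.2.3 and on the form.

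The cost is wording in those sections, one eCRF event category and a few diary lines. No visit or procedure is added. The downside is a few minor events to record and rate among up to 50 participants.
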